## 7.2.4.1 Tumor collection

### 7.2.4.1.1 Potential predictive markers

The status of immune checkpoint targets and cell populations will be analyzed in newly obtained or archival tumor sample. Expression and localization of biomarkers including but not limited to PD-L1 and CD8+ TIL counts may be measured by immunohistochemistry (IHC) or using additional techniques deemed suitable. Other related biomarkers may also be analyzed from this sample, depending on sample availability, resources, and patient's outcomes and as new scientific evidence becomes available.

Submission of an archival specimen or newly obtained tumor sample (formalin fixed, in ethanol) will be requested at screening/baseline (a fresh tumor sample is preferred), unless agreed differently between Novartis and the Investigator. A corresponding pathology report should be included along with the archival samples.

Archived tumor samples may be returned to the pathology laboratory at the end of the study, or at any time, at the request of the Investigator.

### 7.2.4.1.2 Pharmacodynamic markers (patients in PDR001 arm)

#### **Pharmacodynamic assessments in tumor samples**

For pharmacodynamic assessments, collection of evaluable newly obtained on-treatment tumor samples between Cycle 3 Day 1 and End of Treatment is recommended, and if site of disease is accessible. Exceptions may be made on a case by case basis after discussion between Novartis and the Investigator.

[figure not shown]
The pre- and on-treatment paired tumor samples will be used to assess PDR001 target modulation with established immunohistochemical methods and RNA expression analysis.

Additional markers or methods may be utilized if indicated by new findings from the literature as well as from Novartis internal data.

### 7.2.4.2 Blood sample collection (patients in PDR001 arm)

Blood samples will be collected as specified in [Table 7-9](#) to characterize markers of activation in immune cells and circulating levels of cytokine in plasma.

All blood samples will be collected and processed as described in the [\[CPDR001X2201 Laboratory Manual\]](#).

## 8 Safety monitoring and reporting

### 8.1 Adverse events

#### 8.1.1 Definitions and reporting

An adverse event is defined as the appearance of (or worsening of any pre-existing) undesirable sign(s), symptom(s), or medical condition(s) that occur after patient's signed informed consent has been obtained. For additional details about irAE, please refer to [Section 6.2.2](#).

Abnormal laboratory values or test results occurring after informed consent constitute adverse events only if they induce clinical signs or symptoms, are considered clinically significant, require therapy (e.g., hematologic abnormality that requires transfusion or hematological stem cell support), or require changes in study medication(s).

Adverse events that begin or worsen after informed consent should be recorded in the Adverse Events eCRF. Conditions that were already present at the time of informed consent should be recorded in the Medical History of the patient's eCRF. Adverse event monitoring should be continued for at least 30 days following the last dose of chemotherapy and 150 days following the last dose of PDR001 treatment. Adverse events (including lab abnormalities that constitute AEs) should be described using a diagnosis whenever possible, rather than individual underlying signs and symptoms. When a clear diagnosis cannot be identified, each sign or symptom should be reported as a separate Adverse Event.

Adverse events will be assessed according to the Common Terminology Criteria for Adverse Events (CTCAE) version 4.03. If CTCAE grading does not exist for an adverse event, the severity of mild, moderate, severe, and life-threatening, corresponding to Grades 1 - 4, will be used. CTCAE Grade 5 (death) will not be used in this study (but is collected as a seriousness criterion); rather, information about deaths will be collected through a Death form.

The occurrence of adverse events should be sought by non-directive questioning of the patient during the screening process after signing informed consent and at each visit during the study. Adverse events also may be detected when they are volunteered by the patient during the screening process or between visits, or through physical examination, laboratory test, or other assessments. As far as possible, each adverse event should be evaluated to determine:

1. The severity grade (CTCAE Grade 1-4)
2. Its duration (Start and end dates)
3. Its relationship to the study treatment (Reasonable possibility that AE is related: No, Yes)
4. Action taken with respect to study or investigational treatment (none, dose adjusted, temporarily interrupted, permanently discontinued, unknown, not applicable)
5. Whether medication or therapy was given (no concomitant medication/non-drug therapy, concomitant medication/non-drug therapy)

6. Outcome (not recovered/not resolved, recovered/resolved, recovering/resolving, recovered/resolved with sequelae, fatal, unknown)
7. Whether it is serious, where a serious adverse event (SAE) is defined as in [Section 8.2.1](#). and which seriousness criteria have been met.

All adverse events should be treated appropriately. If a concomitant medication or non-drug therapy is given, this action should be recorded on the Adverse Event eCRF.

Once an adverse event is detected, it should be followed until its resolution or until it is judged to be permanent, and assessment should be made at each visit (or more frequently, if necessary) of any changes in severity, the suspected relationship to the study treatment, the interventions required to treat it, and the outcome.

Progression of malignancy (including fatal outcomes), if documented by use of appropriate method (for example, as per irRC or as per RECIST), should not be reported as a serious adverse event.

Adverse events separate from the progression of malignancy (example, deep vein thrombosis at the time of progression or hemoptysis concurrent with finding of disease progression) will be reported as per usual guidelines used for such events with proper attribution regarding relatedness to the drug.

After initiation of new post-treatment antineoplastic therapy, only AEs suspected to be related to study treatment will be collected in the Adverse Events CRF.

## **8.1.2 Laboratory test abnormalities**

### **8.1.2.1 Definitions and reporting**

Laboratory abnormalities that constitute an Adverse event in their own right (are considered clinically significant, induce clinical signs or symptoms, require concomitant therapy or require changes in study treatment), should be recorded on the Adverse Events eCRF. Whenever possible, a diagnosis, rather than a symptom should be provided (e.g. anemia instead of low hemoglobin). Laboratory abnormalities that meet the criteria for Adverse Events should be followed until they have returned to normal or an adequate explanation of the abnormality is found. When an abnormal laboratory or test result corresponds to a sign/symptom of an already reported adverse event, it is not necessary to separately record the lab/test result as an additional event.

Laboratory abnormalities, that do not meet the definition of an adverse event, should not be reported as adverse events. A Grade 3 or 4 event (severe) as per CTCAE does not automatically indicate a SAE unless it meets the definition of serious as defined below and/or as per investigator's discretion. A dose hold or medication for the lab abnormality may be required by the protocol in which case the lab abnormality would still, by definition, be an adverse event and must be reported as such.

## 8.2 Serious adverse events

### 8.2.1 Definitions

Serious adverse event (SAE) is defined as one of the following:

- Is fatal or life-threatening
- Results in persistent or significant disability/incapacity
- Constitutes a congenital anomaly/birth defect
- Is medically significant, i.e., defined as an event that jeopardizes the patient or may require medical or surgical intervention to prevent one of the outcomes listed above
- Requires inpatient hospitalization or prolongation of existing hospitalization,
- Note that hospitalizations for the following reasons should not be reported as serious adverse events:
  - Routine treatment or monitoring of the studied indication, not associated with any deterioration in condition
  - Elective or pre-planned treatment for a pre-existing condition that is unrelated to the indication under study and has not worsened since signing the informed consent
  - Social reasons and respite care in the absence of any deterioration in the patient's general condition
- Note that treatment on an emergency outpatient basis that does not result in hospital admission and involves an event not fulfilling any of the definitions of a SAE given above is not a serious adverse event.

Progression of underlying malignancy is not reported as an adverse event if it is clearly consistent with the suspected progression of the underlying cancer as defined by RECIST or irRC. Hospitalization due solely to the progression of underlying malignancy should NOT be reported as a serious adverse event.

Clinical symptoms of progression may be reported as adverse events if the symptom cannot be determined as exclusively due to the progression of the underlying malignancy, or does not fit the expected pattern of progression for the disease under study.

Symptomatic deterioration may occur in some patients. In this situation, progression is evident in the patient's clinical symptoms, but is not supported by the tumor measurements. Or, the disease progression is so evident that the investigator may elect not to perform further disease assessments. In such cases, the determination of clinical progression is based on symptomatic deterioration. These determinations should be a rare exception as every effort should be made to document the objective progression of underlying malignancy.

If there is any uncertainty about an adverse event being due only to the disease under study, it should be reported as an AE or SAE.

### 8.2.2 Reporting

SAE collection will start upon signing the informed consent whether the patient is a screen failure or not. SAEs will be followed until resolution or until clinically relevant improvement or stabilization.

To ensure patient safety, every SAE, regardless of suspected causality, occurring after the patient has provided informed consent and until at least 30 days after the patient has stopped chemotherapy and 150 days after the patient has stopped PDR001 treatment must be reported to Novartis within 24 hours of learning of its occurrence.

Any SAEs experienced after this 30 days in Chemotherapy arm or 150 days in PDR001 treatment period should only be reported to Novartis if the investigator suspects a causal relationship to the study treatment. If a patient starts a post treatment antineoplastic therapy, then only SAEs suspected to be related to study treatment will be reported. Recurrent episodes, complications, or progression of the initial SAE must be reported as follow-up to the original episode within 24 hours of the investigator receiving the follow-up information. An SAE occurring at a different time interval or otherwise considered completely unrelated to a previously reported one should be reported separately as a new event.

The follow-up information should describe whether the event has resolved or continues, if and how it was treated, and whether the patient continued or withdrew from study participation.

Information about all SAEs (either initial or follow-up information) is collected and recorded within the Electronic Data Capture (EDC) system. Data are required to be entered in English by designated investigator site staff in the eSAE Case Report Form (CRF). The investigator must assess the relationship to each specific component of study treatment (if study treatment consists of several drugs).

SAEs (initial and follow-up) that are recorded electronically in the EDC system should be entered and saved within 24 hours of awareness of the SAE. Data required for safety reporting will be transferred directly to the Novartis Chief Medical Office and Patient Safety (CMO&PS) Department. Follow-up information should be provided by updating the eSAE Case Report Form.

Automatic validation procedures within the system check for data discrepancies during and after data entry and, by generating appropriate error messages, allow the data to be confirmed or corrected online by the designated investigator site staff.

CMO&PS staff review the data entered into the eSAE CRFs for completeness and accuracy and instruct the site personnel to make any required corrections or additions. Queries are sent to the investigational site using an electronic data query. Designated investigator site staff is required to respond to the queries and confirm or correct the data.

The Investigator must certify that the data entered into the electronic eSAE Report Forms are complete and accurate prior to database lock. After database lock, the investigator will receive copies of the eSAE data for archiving at the investigational site.

The paper SAE Form may also be used in case of technical emergencies in order to report an SAE within 24 hours. As soon as the technical issues are overcome, the SAE should also be

entered via the eSAE CRF. The paper SAE Form may also be used for all new and follow up cases at the request of Novartis.

If the SAE is not previously documented in the [PDR001 Investigator's Brochure] or Package Insert (new occurrence) and is thought to be related to the Novartis study treatment, an oncology Novartis CMO&PS department associate may urgently require further information from the investigator for Health Authority reporting. Novartis may need to issue an Investigator Notification (IN), to inform all investigators involved in any study with the same drug that this SAE has been reported. Suspected Unexpected Serious Adverse Reactions (SUSARs) will be collected and reported to the competent authorities and relevant ethics committees in accordance with Directive 2001/20/EC or as per national regulatory requirements in participating countries.

### **8.3 Pregnancies**

To ensure patient safety, each pregnancy occurring while the patient is on study treatment must be reported to Novartis within 24 hours of learning of its occurrence. The pregnancy should be followed up to determine outcome, including spontaneous or voluntary termination, details of the birth, and the presence or absence of any birth defects, congenital abnormalities, or maternal and/or newborn complications. After the mother has provided consent, the newborn will be followed-up for 12 months.

When pregnancy occurs in a patient in the study, as general rule the study drug must be discontinued, though the patient may stay in the study and follow the assessments, if she wishes to do so. All assessments that are considered as a risk during pregnancy must not be performed. The patient may continue all other protocol assessments. In exceptional cases, such as a women responding to the lifesaving treatment, the study drug can be continued.

Pregnancy should be recorded on a Clinical Trial Pregnancy Form and reported by the investigator to the oncology Novartis CMO&PS Department. Pregnancy follow-up should be recorded on the same form and should include an assessment of the possible relationship to the investigational treatment and any pregnancy outcome. Any SAE experienced during pregnancy must be reported on the SAE Report Form.

Pregnancy outcomes should be collected for the female partners of any males who took study treatment in this study. Consent to report information regarding these pregnancy outcomes should be obtained from the mother.

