9. Receiving treatment with systemic steroid therapy or any immunosuppressive therapy, other than replacement-dose steroids < 10mg/day prednisone in the setting of adrenal insufficiency. Topical, inhaled, nasal and ophthalmic steroids are not prohibited.
10. Use of any vaccines against infectious diseases (e.g. varicella, pneumococcus) or investigational therapeutic cancer vaccines within 4 weeks of initiation of study treatment.
11. Major surgery within 2 weeks of the first dose of study treatment (mediastinoscopy, insertion of a central venous access device, and insertion of a feeding tube are not considered major surgery).
12. Radiotherapy within 2 weeks of the first dose of study treatment, except for palliative radiotherapy to a limited field, such as for the treatment of bone pain or a focally painful tumor mass.

13. Participation in an interventional, investigational study within 2 weeks of the first dose of study treatment, unless agreed otherwise with Novartis.
  14. Presence of  $\geq$  CTCAE grade 2 toxicity (except alopecia, peripheral neuropathy and ototoxicity, which are excluded if  $\geq$  CTCAE grade 3) due to prior cancer therapy, unless agreed otherwise with Novartis.
  15. Use of hematopoietic colony-stimulating growth factors (e.g. G-CSF, GM-CSF, M-CSF)  $\leq$  2 weeks prior to start of study drug. An erythroid stimulating agent is allowed as long as it was initiated at least 2 weeks prior to the first dose of study treatment and the patient is on a stable dose.
  16. Pregnant or lactating women, where pregnancy is defined as the state of a female after conception and until the termination of gestation, confirmed by a positive hCG laboratory test.
  17. Women of child-bearing potential, defined as all women physiologically capable of becoming pregnant, unless they are using highly effective methods of contraception during dosing and for 150 days after the last dose of PDR001. Highly effective contraception methods include:
    - Total abstinence (when this is in line with the preferred and usual lifestyle of the patient. Periodic abstinence (e.g., calendar, ovulation, symptothermal, post-ovulation methods) and withdrawal are not acceptable methods of contraception

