### 7.1.3 Discontinuation of study treatment

Patients may voluntarily discontinue from the study treatment for any reason at any time. If a patient decides to discontinue from the study treatment, the investigator should make a reasonable effort (e.g. telephone, e-mail, letter) to determine the primary reason for this decision and record this information in the patient's chart and on the appropriate eCRF. They may be considered discontinued if they state an intention to withdraw or fail to return for visits.

The investigator should discontinue study treatment for a given patient if, on balance, he/she believes that continuation would be detrimental to the patient's well-being.

Study treatment may be discontinued under the following circumstances:

- Adverse event
- Lost to follow-up
- Physician's decision
- Progressive disease as per irRC (not as per RECIST v1.1; patients treated with PDR001)
- Progressive disease as per RECIST v1.1 (patients treated with chemotherapy)
- Confirmed Complete response as per RECIST v1.1 (patients treated with PDR001)
- Study terminated by Novartis
- Patient/guardian decision
- Protocol deviation
- Technical problems

Study treatment must be discontinued if any of the following occur:

- Death
- Pregnancy

Patients who discontinue study treatment should undergo as soon as possible and within 14 days of the last dose of study drug or within 14 days of the decision to discontinue study treatment, an End of Treatment (EoT1) visit and then be discontinued from the study treatment (please refer to [Table 7-1](#) and [Table 7-3](#) for list of assessments to be performed).

Patients in the control arm, who switch to PDR001 treatment, should have an EoT visit (EoT2) once they are discontinued from PDR001 treatment (please refer to [Table 7-3](#) for list of assessments to be performed).

If the decision to discontinue the patient occurs at a regular scheduled visit, that visit may become the EoT visit rather than having the patient return for an additional visit. An End of Treatment Phase Disposition eCRF should be completed, giving the reason for stopping the study treatment. End of treatment/Premature withdrawal visit is not considered as the end of the study. The investigator must also contact IRT to register the patient's discontinuation from study treatment.

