### 7.2.2.5 Laboratory evaluations

All laboratory parameters assessed for safety purposes will be evaluated locally (except Cytokines, Serology and EBV test examinations that will be evaluated centrally). Refer to [Table 7-6](#) for a summary of the parameters to be evaluated.

More frequent evaluations may be performed at the investigator's discretion if medically indicated; results should be recorded as unscheduled laboratory assessments.

Novartis will be provided with a copy of the laboratory certification and tabulation of the normal ranges for each parameter required. In addition, if at any time a patient has laboratory parameters obtained from a different outside laboratory, Novartis must be provided with a copy of the certification and a tabulation of the normal ranges for that laboratory.

All females of childbearing potential will have a serum pregnancy test at screening/baseline and/or within  $\leq 72$  hours before first dose of study treatment, day 1 of each cycle and at EOT visit. A urine or serum pregnancy test should be performed every month during and at the end of the safety follow-up period. If the patient is not coming to the clinic for the safety follow-up visits, a urine or serum pregnancy test will be performed at home or at a local doctor's office monthly and the results will be communicated to the site staff. The result will be recorded only in the source documentation, not in the CRF. A positive pregnancy test requires immediate discontinuation of study treatment. In addition, refer [Section 8.3](#) for follow-up and reporting Pregnancies.

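### The protocol gives conflicting rules on dosing in pregnancy: Section 8.3 allows an exception that Sections 7.1.3 and 7.2.2.5 do not

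*Protocol*

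**What the plan says.** Three sections of the current protocol text govern dosing once a patient is pregnant.

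- **Section 7.1.3** separates reasons for which treatment *may* be stopped from those for which it *must* be. The second list opens with "Study treatment must be discontinued if any of the following occur" and has two entries, death and pregnancy. It states no exception.
- **Section 7.2.2.5** says: "A positive pregnancy test requires immediate discontinuation of study treatment". It then refers the reader to Section 8.3 "for follow-up and reporting Pregnancies".
- **Section 8.3** says that on pregnancy "as general rule the study drug must be discontinued". It lets the patient stay in the study for assessments, and adds: "In exceptional cases, such as a women responding to the lifesaving treatment, the study drug can be continued". On notification, it says "each pregnancy occurring while the patient is on study treatment must be reported to Novartis within 24 hours of learning of its occurrence".

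**The concern.** An investigator treating a pregnant woman who is responding to PDR001 has to decide whether to give the next infusion. Sections 7.1.3 and 7.2.2.5 say no. Section 8.3 says it can be given in an exceptional case, and its own example is a patient who is responding. The text therefore supports two readings: Section 8.3 qualifies the other two, or the other two are absolute. Different sites could act differently and each point to the protocol.

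What is at stake is patient and fetal safety and consistent conduct. Section 11.3 describes the risk to the fetus as unknown. The exception has no stated control: Section 8.3 requires the sponsor to be told, but being told is not the same as approving, and neither an approver nor re-consent is mentioned. Table 6-2, by contrast, makes its exception for Grade 4 endocrinopathy subject to the medical monitor's approval.

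**Working it through.** The point turns on wording, so the check is to set the texts side by side and look for anything that reconciles them.

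| Protocol section | Default | Exception | Link to another section |
|---|---|---|---|
| 7.1.3 | Stopping is mandatory | None | None to 8.3 |
| 7.2.2.5 | Stop immediately on a positive test | None | To 8.3, for follow-up and reporting |
| 8.3 | Stop, as a general rule | Drug may continue in exceptional cases | None to 7.1.3 or 7.2.2.5 |

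**Do the terms separate the rules?** Section 8.3 speaks of study drug; the other two speak of study treatment. SAP Section 2.1.1 defines study drug as PDR001 and study treatment as PDR001 and chemotherapy. PDR001 therefore falls under both terms, and the rules overlap for any patient receiving it.

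**Does the pointer bring in the exception?** The pointer in Section 7.2.2.5 is worded as an addition to the stop rule and names only follow-up and reporting. It does not qualify the rule.

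**Does any text set an order of precedence?** None was found. As background, the Amendment 03 rationale says Section 7.1.3 was clarified specifically to separate optional from mandatory reasons. In the current text pregnancy is on the mandatory side.

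**Does Appendix 1 settle it?** Section 14.1.4.2 lists pregnancy among reasons for which patients may discontinue. That list is generic and also contains death, so it neither resolves the conflict nor counts as a further one.

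**How many patients could be affected?** The Amendment 06 study status gives the ongoing patients at 21-May-2019, all on PDR001:

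- 11 randomized to PDR001 + 1 crossover = 12 ongoing
- 12 / 122 randomized = 9.8%

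This is an upper bound for that date only. The number of women of child-bearing potential among the 12 is not given.

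**What lowers the chance further?** Section 5.3 excludes women of child-bearing potential "unless they are using highly effective methods of contraception during dosing and for 150 days after the last dose of PDR001". Section 7.2.2.5 requires a serum pregnancy test at "day 1 of each cycle and at EOT visit".

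**The case against.** The strongest reply is that Section 8.3 is the section devoted to managing a pregnancy, while Section 7.1.3 offers one word in a list and Section 7.2.2.5 concerns laboratory tests. The drafter evidently meant a rule with an exception, and an investigator who follows the pointer will find it. On that view the defect is only a missing cross-reference. This is a fair reading, but it does not settle the matter. No text says Section 8.3 prevails, and the sentence in Section 7.2.2.5 is itself specific to pregnancy, so preferring the specific to the general does not choose between them. Nor does the protocol let a site resolve the question by asking: Section 12 permits no authorized deviations and tells investigators not to request approval of one.

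A second objection is that the patient count is dated. SAP Section 4.1 says that by the start of the pandemic the vast majority of patients had stopped treatment and completed safety follow-up. Under protocol Section 4.3 the study ends no later than 24 months after the last randomized patient's first dose, which was on 03-Aug-2018; that is about August 2020. This stands as a limit. The figure of 12 describes 21-May-2019, not the position at final reporting or exposure over the whole trial, and an amendment helps only while patients are still being dosed.

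A third objection is that deleting the exception removes a clinical option the protocol expressly wrote in. That also has force, and it is why a route that keeps the exception is set out as an alternative. The missing approver and the silence on re-consent concern how the exception is governed rather than the inconsistency itself, but they matter if it is kept. The 24-hour notification does give the sponsor an opportunity to intervene.

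**Conclusion.** The concern holds and is minor. Two sections require PDR001 to be stopped in pregnancy without exception, a third allows it to continue, and nothing in the protocol reconciles them. The shared default of stopping is not in doubt.

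The practical reach is small: an on-treatment pregnancy in which someone considers invoking the exception. At 21-May-2019 that could concern at most 12 patients, and no pregnancy is reported. The conclusion rests on the current wording of the three sections and on the SAP's definitions of study drug and study treatment. It does not depend on which rule the sponsor intended. The primary endpoint, power, sample size and error rate are not touched.

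**What to change.** **Default.** In Section 8.3, delete the words that make stopping only a general rule, and delete the exception sentence. The section then requires discontinuation, as Sections 7.1.3 and 7.2.2.5 do. The text letting the patient remain in the study for assessments can stay. The cost is two deletions in one paragraph.

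**Alternative, if the sponsor wants the exception.** State it in Sections 7.1.3, 7.2.2.5 and 8.3, conditional on documented medical monitor approval and patient re-consent before the next dose. This means edits to three sections. It may also need a consent document reviewed by the IRB/IEC; the consent form is separate from the protocol (Section 11.3) and was not available here.

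Either version can go into the next written amendment under Section 12.1. Neither changes the design, visits or analysis.
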